### 10.2 Formulation, Packaging, and Labeling

The active ingredient RZL-012 drug substance was manufactured by Cambrex, NC, USA. RZL-012 drug product was manufactured in Patheon (Italy) and packed and labeled at ThermoFischer,

USA. The drug product is provided in vials of 240 mg/4.8 mL (50 mg/mL) and 163mg/4.8 mL (34 mg/ml).

The active ingredient and formulation manufacturing and packing were in accordance with cGMPs.

RZL-012 will be provided in 2 strengths of 240 mg/4.8 mL (50 mg/mL) and 163 mg/4.8 mL (34 mg/mL).

The placebo is a ready to use liquid to be injected into the subcutaneous fat, supplied in a 1 vial kit. Each vehicle vial contains 4.8 mL solution volume.

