## 8.5 Drug Administration

RZL-012 or placebo will be supplied as a single treatment in multiple sites of injection (32±4 injections). The injection dosing regimen and technique is crucial for the therapy safety.

The following procedures prior to injection into the SMF will be applied:

1. The lower face and anterior neck will be cleaned with an appropriate topical antiseptic.
2. Ice/cold pack or topical local anesthesia (i.e., lidocaine cream) may be used prior to drug administration to enhance subject's comfort.
3. The treatment area will be bounded superiorly by a line 1 cm inferior to the mandibular margin, laterally by the sternocleidomastoid muscles, and inferiorly by the hyoid bone.
4. Injection grid pattern will be applied by pressing the grid firmly onto the clean, dry skin, with the printed grid pattern facing the skin. The grid paper backing will be thoroughly wetted with a cotton pad soaked with sterile water. After 15 seconds, the grid cover will be peeled off.
5. An area of 32±4 adjacent injection points will be determined following the Investigator's evaluation.
6. Syringes will be filled with 1 mL RZL-012 high dose or low dose or placebo and the number of syringes will be compatible with the total volume of injection. Up to six (6) syringes for a total volume of 5.4 mL will be used.
7. All injections will be administered perpendicularly in 90 degrees, using a 1 mL Luer-lock syringe and a 29G x 1/2" needle, respectively.
8. The hole of the needle should be pointing into the fat layer and the injection direction should be towards the earth. An attempt to pull the plunger should be made prior to injecting to ensure no blood is coming out. If so, the plunger should be pushed down to inject 0.15 ml the medicine. The formulation is viscous; therefore, resistance is expected during injection.
9. Immediately following completion of the injections, an ice/cold pack will be applied for immediate pain relief. It will be held by the subject for at least two (2) minutes.
10. The Investigator will record the number of injections administered for each subject.

The injection pattern used will be based on an existing grid in the shape of the submental area, where distance between injection rows will be 1 cm and distance between the injection columns will be 1 cm.

The number of injections for each subject will be determined by the Investigator according to fullness of SMF but will not be lower than 28 injections or higher than 36 injections.

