Each RZL-012 kit contains 2 vials that will be assigned to each subject:

- RZL-012 low dose will be provided in vials of 163 mg/4.8 mL (34 mg/mL)
- RZL-012 high dose will be provided in vials of 240 mg/4.8 mL (50 mg/mL)

Treatment with placebo will be conducted in the same manner as above.

The calendar date and 24-hour clock time of all doses will be recorded on the CRF.

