### **10.4 Study Drug Administration**

Each kit containing 2 vials must be kept and handled at room temperature. The vials should be manually shaken prior to injection.

1 mL Luer-lock syringes with RZL-012 solution should be filled with 29 G ½" sterile needle for a maximal low dose of 183.6 mg and a maximal high dose of 270 mg. Two vials will be used for each subject. Breached vials will not be used for another subject. Each vial must be placed back into the container. All open vials will be kept until the end of study when the Sponsor will determine if study drug should be returned or destroyed.

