## **10.6 Accountability of Study Drugs**

All study drugs received, dispensed, and returned must be accounted for in the study drug Dispensing Log, including:

- Subject number and initials
- Date study drug was dispensed
- Quantity dispensed
- Quantity returned
- Quantity wasted, as applicable

All study drug received and dispensed by the Investigator will be inventoried and accounted for throughout the study. The study drug must be stored in a restricted area with limited access. Contents of the study drug containers must not be combined. Used sprayers will be accounted for and disposed appropriately.

The Investigator must maintain an accurate, up to date Dispensing Log for all study drugs supplied by the Sponsor. Study drug dispensed for all subjects must be recorded on the Drug Accountability Form. The study drug Dispensing Log and remaining drug inventory will be reviewed at each monitoring visit by the Sponsor-designated clinical monitor.

The study drug supplied for this study is for use only in subjects properly consented and enrolled into this protocol. Study drugs must be kept in a secure location physically separated from standard clinic or office drug supplies.

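### Section 10.2 packs placebo as a 1-vial kit while Sections 8.5 and 10.4 describe 2-vial kits; if 10.2 is followed, kit format or number differs between placebo and active, a possible risk to the blind

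*Protocol*

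**What the plan says.** Four parts of the protocol bear on how many vials a placebo subject receives.

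- **Section 10.2** says placebo is "supplied in a 1 vial kit. Each vehicle vial contains 4.8 mL solution volume".
- **Section 8.5** says of the active product: "Each RZL-012 kit contains 2 vials that will be assigned to each subject". After listing the two RZL-012 strengths it adds: "Treatment with placebo will be conducted in the same manner as above".
- **Section 10.4** names no arm for kit contents: "Each kit containing 2 vials must be kept and handled at room temperature". It also says: "Two vials will be used for each subject". The dose sentence in that section mentions only the two RZL-012 doses.
- **Section 10.3** speaks of the RZL-012 kit and the placebo vehicle as separate items and gives no vial count.

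Every arm receives 0.15 mL per injection (Section 2.4.1). The number of injections depends on submental fullness, "but will not be lower than 28 injections or higher than 36 injections" (Section 8.5). Section 2.4.1 caps the volume at 5.4 mL in all groups.

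Section 8.3 blinds the Investigator, site staff and subjects. Section 4.11 has the Investigator score the C-CAT. Section 10.6 says: "All study drug received and dispensed by the Investigator will be inventoried and accounted for throughout the study". It also requires a dispensing log with quantities dispensed and returned for each subject.

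**The concern.** A site reading Section 10.2 would expect one vial per placebo kit. The same site reading Section 10.4 would expect two. If supply was packed to Section 10.2, a placebo subject's kit does not match an active subject's kit in vial count or in the number of kits used. The difference would separate placebo from active, though not high dose from low dose, and placebo against high dose is the primary comparison.

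The blind matters here because the primary endpoint is a graded clinical judgement made by the Investigator, who under Section 10.6 also receives, dispenses and logs the drug. Section 10.4 has used vials put back in their container and opened vials kept to the end of the study, so a difference in vial count would remain on site. Neither document says that kits look alike across arms or that someone unblinded prepares the syringes.

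A second question is whether the placebo volume is enough. An injection count cut short for lack of vehicle would no longer follow fullness, which is how Section 8.5 sets it.

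**Working it through.** **Inputs.** Volume per injection 0.15 mL (Section 2.4.1). Injections per subject 28 to 36 (Section 8.5). Vial volume 4.8 mL for both RZL-012 strengths and for placebo (Section 10.2). Vials per kit: 1 for placebo (Section 10.2), 2 for RZL-012 (Section 8.5), 2 with no arm named (Section 10.4). Placebo group size 45 (Section 12.1).

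**Step 1: reproduce the plan's maximum.** Volume = injections × 0.15 mL. 36 × 0.15 = 5.4 mL, as stated. The maximum doses also agree: 36 × 7.5 = 270 mg and 36 × 5.1 = 183.6 mg.

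**Step 2: capacity.** One vial: 4.8 / 0.15 = 32 injections. Two vials: 9.6 / 0.15 = 64 injections.

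**Step 3: one vial against the permitted range.** Shortfall = (injections × 0.15) − 4.8, before any loss.

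| Injections | Volume needed (mL) | Shortfall (mL) | Share of volume needed |
|---|---|---|---|
| 28 | 4.20 | 0 | 0 |
| 32 | 4.80 | 0 | 0 |
| 33 | 4.95 | 0.15 | 3.0% |
| 34 | 5.10 | 0.30 | 5.9% |
| 35 | 5.25 | 0.45 | 8.6% |
| 36 | 5.40 | 0.60 | 11.1% |

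Four of the nine permitted counts (33 to 36) exceed one vial. Overfill of 0.60 mL, or 0.60 / 4.8 = 12.5%, would be needed for one vial to cover 36. No overfill is stated.

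**Step 4: the three ways to read the text.**

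| Reading | Placebo volume | Shortage? | Placebo kits differ from active? |
|---|---|---|---|
| Section 10.4 covers all arms: one 2-vial kit | 9.6 mL | No | Not in vial or kit count; Section 10.2 is simply wrong |
| Two 1-vial placebo kits per subject | 9.6 mL | No | Yes, in number and format of kits |
| One 1-vial placebo kit per subject | 4.8 mL | Yes, above 32 injections | Yes, in vial count |

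The third reading contradicts Section 10.4's two vials per subject. The second meets that sentence but conflicts with Section 10.4's description of the kit, if that description includes placebo. Under each reading at least one section needs correcting or completing.

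**The case against.** The strongest reply is that Section 10.4 already settles the count. It governs administration, names no arm, and allots two vials to each subject. Its dose sentence lists only RZL-012, but placebo has no milligram dose to list, so that omission proves little. Section 10.2 describes packaging and never says one kit per subject. This stands as far as volume goes: a reader might infer that placebo subjects will run out of vehicle, and the documents do not support that unless Section 10.4 is set aside.

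A reader might also infer a larger shortage from the instruction "Syringes will be filled with 1 mL RZL-012 high dose or low dose or placebo", since 1 mL is not a whole number of 0.15 mL injections. That does not follow. The same step matches the number of syringes to the total volume and allows up to six for 5.4 mL, which is 5.4 / 6 = 0.9 mL each, or exactly six injections with nothing left over. Loss in syringes is avoidable and should not be added to the shortfall.

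Finally, a reader might infer that the Investigator is unblinded. The documents do not show this. It would require that placebo is actually packed as Section 10.2 says, that the rater sees the kits or the log, and that the rater knows which format is placebo. Masking may be covered in packaging or pharmacy documents outside this set.

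The inconsistency itself remains. Nothing in the protocol or SAP says which section prevails on kit format, and Section 8.3 states the blind without saying how the kits preserve it.

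**Conclusion.** The protocol contradicts itself on placebo supply, and this should be corrected. If Section 10.2 reflects how placebo is packed, kit format or kit number distinguishes placebo from active. That is a possible risk to the blind of the person who rates the primary endpoint; its size cannot be estimated from the documents.

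The shortage is conditional. It arises only if a single 1-vial kit is used per subject, contrary to Section 10.4. It is then 0.15 to 0.60 mL at 33 to 36 injections (3.0% to 11.1% of the volume needed), assuming no overfill and no loss. How many subjects would need more than 32 injections is not given. With two vials there is no shortage at any permitted count. Active dose, sample size and planned tests are unaffected.

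**What to change.** - **Section 10.2:** state that placebo is supplied in kits of two 4.8 mL vials, matching the RZL-012 kits in vial count and appearance.
- **Sections 8.5 and 10.4:** state that one 2-vial kit is assigned to each subject in all three arms.

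If placebo is already packed this way, the cost is wording only. If 1-vial kits have been made, it is about 45 extra placebo vials (one more for each of 45 placebo subjects) plus overage, and repacking.

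A separate clerical correction can go into the same amendment. The placebo cell in Table 4 and in the synopsis dosing table gives 5.4 ± 0.6 mL, which would allow 5.4 + 0.6 = 6.0 mL. It should read 4.8 ± 0.6 mL with a maximum of 5.4 mL, in line with Sections 2.2 and 2.4.1.

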### **10.3 Receipt, Storage and Stability of RZL-012**

The RZL-012 kit and placebo vehicle will be stored in the site at monitored room temperature conditions (15 - 30 degrees Celsius) protected from light.

Drug product stability has successfully reached three (3) years. Site inventory will be managed by the Sponsor according to accumulating stability data. Suitability of the product's expiration date must take into consideration and comply with First In First Out (FIFO) principals.

### **10.4 Study Drug Administration**

Each kit containing 2 vials must be kept and handled at room temperature. The vials should be manually shaken prior to injection.

1 mL Luer-lock syringes with RZL-012 solution should be filled with 29 G ½" sterile needle for a maximal low dose of 183.6 mg and a maximal high dose of 270 mg. Two vials will be used for each subject. Breached vials will not be used for another subject. Each vial must be placed back into the container. All open vials will be kept until the end of study when the Sponsor will determine if study drug should be returned or destroyed.

### **10.5 Ordering and Distribution of Study Drug**

RZL-012 drug product was manufactured in Patheon (Italy) and packed and labeled at ThermoFischer, USA. The drug product is provided in vials of 240 mg/4.8 mL (50 mg/mL) and 163mg/4.8 mL (34 mg/ml).

RZL-012 will be dispensed to the sites under monitored conditions by ThermoFischer USA.

The active ingredient and formulation manufacturing and packing were in accordance with current Good Manufacturing Practices (cGMPs).

## **10.6 Accountability of Study Drugs**

All study drugs received, dispensed, and returned must be accounted for in the study drug Dispensing Log, including:

- Subject number and initials
- Date study drug was dispensed
- Quantity dispensed
- Quantity returned
- Quantity wasted, as applicable

All study drug received and dispensed by the Investigator will be inventoried and accounted for throughout the study. The study drug must be stored in a restricted area with limited access. Contents of the study drug containers must not be combined. Used sprayers will be accounted for and disposed appropriately.

The Investigator must maintain an accurate, up to date Dispensing Log for all study drugs supplied by the Sponsor. Study drug dispensed for all subjects must be recorded on the Drug Accountability Form. The study drug Dispensing Log and remaining drug inventory will be reviewed at each monitoring visit by the Sponsor-designated clinical monitor.

The study drug supplied for this study is for use only in subjects properly consented and enrolled into this protocol. Study drugs must be kept in a secure location physically separated from standard clinic or office drug supplies.

## **11.0 SAFETY MONITORING AND ADVERSE EVENTS**

### **11.1 Adverse Events**

Data regarding TEAEs will be collected in this study. TEAEs are events that are not present at baseline, or if present at baseline, have worsened in severity.

AEs reported during the trial will be graded, documented, and assessed for relationship to study drug. Specifically, assessment of AEs related to skin condition and injection procedure will be closely monitored, including edema, bruising, dysphasia, dysphonia, erythema, dyspigmentation, induration, numbness, pain, paresthesia, pruritus, skin ulceration and necrosis, injury to the marginal mandibular nerve, vascular and nerve injury and tissue damage to nearby vulnerable anatomic structures..

### **Definition of Adverse Events and Adverse Drug Reactions:**

AEs in the eCRF will be classified according to the most recent FDA definitions and in a manner consistent with International Conference on Harmonization (ICH) guidelines. As such the following definitions will be used:

An AE is any unfavorable and unintended sign, symptom, or disease temporally associated with the use of an investigational (medicinal) product (IP) or other protocol-imposed intervention, regardless of attribution. An AE may include intercurrent illnesses or injuries that represent an exacerbation (increase in frequency, severity, or specificity) of pre-existing conditions (e.g., worsening of asthma). A laboratory abnormality will be reported on the “Adverse Event” case report forms only if it is associated with clinical sequelae or requires therapeutic intervention. Whenever possible, it is preferable to record a diagnosis as the AE term rather than a series of symptoms relating to a diagnosis. AEs will be coded according to the Medical Dictionary for Regulatory Activities (MedDRA) and graded according to the Common Terminology Criteria for Adverse Events (CTCAE) v 5.0 (Table 5).

The reporting period for AEs starts after dosing of study drug and will end at final study visit on Day 84. At study completion, after the Day 84 visit of the last subject, subjects at 3 chosen clinical sites will be followed up at 6 and 12 months after injection to follow safety and duration of efficacy.

If an AE remains unresolved at discharge, subject will be scheduled for a visit that will be held 6-8 weeks after study termination to verify the resolution of AE. On that visit, follow up of efficacy using C-CAT and S-CAT will also be conducted. In case the AE will not resolved following that visit, the subject will be followed, at the Investigator’s discretion, until resolution of the event or until the subject is deemed “lost to follow-up”. AEs assessed by the Investigator as related to study drug and “ongoing” at discharge will be monitored by the Investigator until resolved or until the subject is deemed “lost to follow-up”. SAEs must be followed until resolution by the PI, even if this extends beyond the study-reporting period. Resolution is defined as the return to baseline status or stabilization of the condition with the expectation that it will remain chronic.

The Investigator will assess AEs for severity, relationship to IP, and as to whether the event meets one or more of the definitions of an SAE. The assessments will be recorded on the source documents and AE CRF, using the categories defined below.

Causality Category	Description
Un-related	A clinical event, including laboratory test abnormality, with a temporal relationship to drug administration which makes a causal relationship improbable, and in which other drugs, chemicals or underlying disease provide plausible explanations. For the purpose of this protocol, the term unlikely will be considered not related to study medication and an “Adverse Event”.
Related	A clinical event, including laboratory test abnormality, with a reasonable time sequence to administration of the drug, but which could also be explained by concurrent disease or other drugs or chemicals. Information on drug withdrawal may be lacking or unclear. For the purpose of this protocol, an event that has possible or probable relationship to study medication will be defined as a “Suspected Adverse Drug Reaction”.

In order to classify AEs and diseases, preferred terms will be assigned by the sponsor or its designee to the original terms entered on the CRF, using MedDRA.

For those AEs that are not described on the CTCAE v 5.0, such AEs will be graded on a 5-point scale (mild, moderate, severe) and reported as indicated on the CRF. Intensity of such an AE is defined as follows:

**Table 5: Severity Assessment Terminology for Reporting Adverse Events (CTCAE v 5.0)**

CTCAE Grade	Common Term	Description
1	Mild	Mild; asymptomatic or mild symptoms; clinical or diagnostic observations only; intervention not indicated.
2	Moderate	Moderate; minimal, local or noninvasive intervention indicated; limiting age-appropriate instrumental Assisted Daily Living (ADL).
3	Severe	Severe or medically significant but not immediately life-threatening; hospitalization or prolongation of hospitalization indicated; disabling; limiting self-care ADL.
4	Life-Threatening	Life-threatening consequences; urgent intervention indicated.
5	Death	Death related to AE

## 11.2 Serious Adverse Events

According to the ICH Guidelines for Good Clinical Practice (E6), an SAE is any untoward medical occurrence during the course of a clinical investigation that is characterized by one or more of the following:

- Results in death
- Is life-threatening
- Requires in-subject hospitalization or prolongation of existing hospitalization
- Results in persistent or significant disability/incapacity
- Is a congenital anomaly/birth defect
- Important medical events

Although not an SAE, exposure to study drug during pregnancy, even if no AE is reported in the mother, should be reported within 24 hours.

### 11.2.1 Reporting Requirements for Serious Adverse Events

All SAEs must be reported to the Sponsor by the Investigator, study coordinator, other designated study personnel, or clinical research associate within 24 hours of notification of the SAE. To report such events, an SAE form must be completed by the Investigator and sent within 24 hours by email or fax with relevant information.

Within the 48 hours following the initial report, the Investigator must provide further information on the SAE if available. This should include a copy of the completed SAE form, and any other information that will assist the understanding of the event. Significant new information on ongoing SAEs should be provided promptly as a follow-up.

The Investigator also must report all SAEs promptly to the appropriate IRB/EC as required by the institution within 24 hours or 48 hours if on weekend/holiday.

### **11.2.2 Reporting pregnancy**

Pregnancy testing must be preformed on all women of childbearing potential prior to dosing, and all the results of all pregnancy tests are to be recorded in the eCRF's. All women must have a negative pregnancy test to be enrolled into the study. If a pregnancy test turns positive after study drug treatment, the patient will be discontinued and protocol-required procedures for study discontinuation and follow-up must be preformed. The subject will be followed to determine the outcome of the pregnancy. All women of childbearing potential should be instructed to contact the investigator if they suspect they might be pregnant (e.g. missed or late menstrual period) at any time during the study.

The investigator must notify the sponsor of any pregnancies in accordance with the SAE reporting procedures described in section 11.2.1. Note, while the pregnancy is not considered an AE or an SAE, any pregnancy complication or newborn complication will be reported as an AE or SAE if it meets the criteria. Follow-up information regarding the course of pregnancy, including perinatal and neonatal outcomes and, where applicable, offspring information must be reported on the Pregnancy Outcome eCRF.

### **11.2.3 Recording of Serious Adverse Events**

All SAE information must be recorded on the SAE form provided by the Sponsor. Additional follow-up information (e.g., test results, autopsy, and discharge summary) must be obtained to supplement the SAE report form. A copy of all initial and follow-up reports must be filed with the subject's eCRF.

